Amylase and/or lipase elevation, Grade 2	
 • Continue atezolizumab. • Monitor amylase and lipase weekly. • For prolonged elevation (e.g., > 3 weeks), consider treatment with 10 mg/day oral prednisone or equivalent.
Amylase and/or lipase elevation, Grade 3 or 4	
 • Withhold atezolizumab for up to 12 weeks after event onset. ^a • Refer patient to GI specialist. • Monitor amylase and lipase every other day. • If no improvement, consider treatment with 1–2 mg/kg/day oral prednisone or equivalent. • If event resolves to Grade 1 or better, resume atezolizumab. ^b • If event does not resolve to Grade 1 or better while withholding atezolizumab, permanently discontinue atezolizumab and contact Medical Monitor. ^c • For recurrent events, permanently discontinue atezolizumab and contact Medical Monitor. ^c

GI = gastrointestinal.

^a Atezolizumab may be withheld for a longer period of time (i.e., > 12 weeks after event onset) to allow for corticosteroids (if initiated) to be reduced to ≤ 10 mg/day oral prednisone or equivalent. The acceptable length of the extended period of time must be agreed upon by the investigator and the Medical Monitor.

^b If corticosteroids have been initiated, they must be tapered over ≥ 1 month to ≤ 10 mg/day oral prednisone or equivalent before atezolizumab can be resumed.

^c Resumption of atezolizumab may be considered in patients who are deriving benefit and have fully recovered from the immune-mediated event. Patients can be re-challenged with atezolizumab only after approval has been documented by both the investigator (or an appropriate delegate) and the Medical Monitor.

Appendix 9

Risks Associated with Atezolizumab and Guidelines for Management of Adverse Events Associated with Atezolizumab (cont.)

Table 8 Management Guidelines for Pancreatic Events, Including Pancreatitis (cont.)

Event	Management
Immune-mediated pancreatitis, Grade 2 or 3	
 • Withhold atezolizumab for up to 12 weeks after event onset. ^a • Refer patient to GI specialist. • Initiate treatment with 1–2 mg/kg/day IV methylprednisolone or equivalent and convert to 1–2 mg/kg/day oral prednisone or equivalent upon improvement. • If event resolves to Grade 1 or better, resume atezolizumab. ^b • If event does not resolve to Grade 1 or better while withholding atezolizumab, permanently discontinue atezolizumab and contact Medical Monitor. ^c • For recurrent events, permanently discontinue atezolizumab and contact Medical Monitor. ^c
Immune-mediated pancreatitis, Grade 4	
 • Permanently discontinue atezolizumab and contact Medical Monitor. ^c • Refer patient to GI specialist. • Initiate treatment with 1–2 mg/kg/day IV methylprednisolone or equivalent and convert to 1–2 mg/kg/day oral prednisone or equivalent upon improvement. • If event does not improve within 48 hours after initiating corticosteroids, consider adding an immunosuppressive agent. • If event resolves to Grade 1 or better, taper corticosteroids over ≥ 1 month.

GI = gastrointestinal.

^a Atezolizumab may be withheld for a longer period of time (i.e., > 12 weeks after event onset) to allow for corticosteroids (if initiated) to be reduced to ≤ 10 mg/day oral prednisone or equivalent. The acceptable length of the extended period of time must be agreed upon by the investigator and the Medical Monitor.

^b If corticosteroids have been initiated, they must be tapered over ≥ 1 month to ≤ 10 mg/day oral prednisone or equivalent before atezolizumab can be resumed.

^c Resumption of atezolizumab may be considered in patients who are deriving benefit and have fully recovered from the immune-mediated event. Patients can be re-challenged with atezolizumab only after approval has been documented by both the investigator (or an appropriate delegate) and the Medical Monitor.

Appendix 9

Risks Associated with Atezolizumab and Guidelines for Management of Adverse Events Associated with Atezolizumab (cont.)

DERMATOLOGIC EVENTS

Treatment-emergent rash has been associated with atezolizumab. The majority of cases of rash were mild in severity and self-limited, with or without pruritus. A dermatologist should evaluate persistent and/or severe rash or pruritus. A biopsy should be considered unless contraindicated. Management guidelines for dermatologic events are provided in [Table 9](#).

Table 9 Management Guidelines for Dermatologic Events

Event	Management
Dermatologic event, Grade 1	
 • Continue atezolizumab. • Consider treatment with topical corticosteroids and/or other symptomatic therapy (e.g., antihistamines).
Dermatologic event, Grade 2	
 • Continue atezolizumab. • Consider patient referral to dermatologist. • Initiate treatment with topical corticosteroids. • Consider treatment with higher-potency topical corticosteroids if event does not improve.
Dermatologic event, Grade 3	
 • Withhold atezolizumab for up to 12 weeks after event onset. ^a • Refer patient to dermatologist. • Initiate treatment with 10 mg/day oral prednisone or equivalent, increasing dose to 1–2 mg/kg/day if event does not improve within 48–72 hours. • If event resolves to Grade 1 or better, resume atezolizumab. ^b • If event does not resolve to Grade 1 or better while withholding atezolizumab, permanently discontinue atezolizumab and contact Medical Monitor. ^c
Dermatologic event, Grade 4	
 • Permanently discontinue atezolizumab and contact Medical Monitor. ^c

^a Atezolizumab may be withheld for a longer period of time (i.e., > 12 weeks after event onset) to allow for corticosteroids (if initiated) to be reduced to ≤ 10 mg/day oral prednisone or equivalent. The acceptable length of the extended period of time must be agreed upon by the investigator and the Medical Monitor.

^b If corticosteroids have been initiated, they must be tapered over ≥ 1 month to ≤ 10 mg/day oral prednisone or equivalent before atezolizumab can be resumed.

^c Resumption of atezolizumab may be considered in patients who are deriving benefit and have fully recovered from the immune-mediated event. Patients can be re-challenged with atezolizumab only after approval has been documented by both the investigator (or an appropriate delegate) and the Medical Monitor.

Appendix 9

Risks Associated with Atezolizumab and Guidelines for Management of Adverse Events Associated with Atezolizumab (cont.)

NEUROLOGIC DISORDERS

Myasthenia gravis and Guillain-Barré syndrome have been observed with single-agent atezolizumab. Patients may present with signs and symptoms of sensory and/or motor neuropathy. Diagnostic workup is essential for an accurate characterization to differentiate between alternative etiologies. Management guidelines for neurologic disorders are provided in [Table 10](#).

Table 10 Management Guidelines for Neurologic Disorders

Event	Management
Immune-mediated neuropathy, Grade 1	
 • Continue atezolizumab. • Investigate etiology.
Immune-mediated neuropathy, Grade 2	
 • Withhold atezolizumab for up to 12 weeks after event onset.^a • Investigate etiology. • Initiate treatment as per institutional guidelines. • If event resolves to Grade 1 or better, resume atezolizumab.^b • If event does not resolve to Grade 1 or better while withholding atezolizumab, permanently discontinue atezolizumab and contact Medical Monitor.^c
Immune-mediated neuropathy, Grade 3 or 4	
 • Permanently discontinue atezolizumab and contact Medical Monitor.^c • Initiate treatment as per institutional guidelines.
Myasthenia gravis and Guillain-Barré syndrome (any grade)	
 • Permanently discontinue atezolizumab and contact Medical Monitor.^c • Refer patient to neurologist. • Initiate treatment as per institutional guidelines. • Consider initiation of 1–2 mg/kg/day oral or IV prednisone or equivalent.

^a Atezolizumab may be withheld for a longer period of time (i.e., > 12 weeks after event onset) to allow for corticosteroids (if initiated) to be reduced to ≤ 10 mg/day oral prednisone or equivalent. The acceptable length of the extended period of time must be agreed upon by the investigator and the Medical Monitor.

^b If corticosteroids have been initiated, they must be tapered over ≥ 1 month to ≤ 10 mg/day oral prednisone or equivalent before atezolizumab can be resumed.

^c Resumption of atezolizumab may be considered in patients who are deriving benefit and have fully recovered from the immune-mediated event. Patients can be re-challenged with atezolizumab only after approval has been documented by both the investigator (or an appropriate delegate) and the Medical Monitor.

Appendix 9

Risks Associated with Atezolizumab and Guidelines for Management of Adverse Events Associated with Atezolizumab (cont.)

IMMUNE-MEDIATED MENINGOENCEPHALITIS

Immune-mediated meningoencephalitis is an identified risk associated with the administration of atezolizumab. Immune-mediated meningoencephalitis should be suspected in any patient presenting with signs or symptoms suggestive of meningitis or encephalitis, including, but not limited to, headache, neck pain, confusion, seizure, motor or sensory dysfunction, and altered or depressed level of consciousness.

Encephalopathy from metabolic or electrolyte imbalances needs to be distinguished from potential meningoencephalitis resulting from infection (bacterial, viral, or fungal) or progression of malignancy, or secondary to a paraneoplastic process.

All patients being considered for meningoencephalitis should be urgently evaluated with a CT scan and/or MRI scan of the brain to evaluate for metastasis, inflammation, or edema. If deemed safe by the treating physician, a lumbar puncture should be performed and a neurologist should be consulted.

Patients with signs and symptoms of meningoencephalitis, in the absence of an identified alternate etiology, should be treated according to the guidelines in [Table 11](#).

Table 11 Management Guidelines for Immune-Mediated Meningoencephalitis

Event	Management
Immune-mediated meningoencephalitis, all grades	
• Permanently discontinue atezolizumab and contact Medical Monitor.^a• Refer patient to neurologist.• Initiate treatment with 1–2 mg/kg/day IV methylprednisolone or equivalent and convert to 1–2 mg/kg/day oral prednisone or equivalent upon improvement.• If event does not improve within 48 hours after initiating corticosteroids, consider adding an immunosuppressive agent.• If event resolves to Grade 1 or better, taper corticosteroids over ≥ 1 month.

^a Resumption of atezolizumab may be considered in patients who are deriving benefit and have fully recovered from the immune-mediated event. Patients can be re-challenged with atezolizumab only after approval has been documented by both the investigator (or an appropriate delegate) and the Medical Monitor.

RENAL EVENTS

Immune-mediated nephritis has been associated with the administration of atezolizumab. Eligible patients must have adequate renal function. Renal function, including serum creatinine, should be monitored throughout study treatment. Patients with abnormal renal function should be evaluated and treated for other more common etiologies

Appendix 9

Risks Associated with Atezolizumab and Guidelines for Management of Adverse Events Associated with Atezolizumab (cont.)

(including prerenal and postrenal causes, and concomitant medications such as non-steroidal anti-inflammatory drugs). Refer the patient to a renal specialist if clinically indicated. A renal biopsy may be required to enable a definitive diagnosis and appropriate treatment.

Patients with signs and symptoms of nephritis, in the absence of an identified alternate etiology, should be treated according to the guidelines in [Table 12](#).

Table 12 Management Guidelines for Renal Events

Event	Management
Renal event, Grade 1	
 • Continue atezolizumab. • Monitor kidney function, including creatinine, closely until values resolve to within normal limits or to baseline values.
Renal event, Grade 2	
 • Withhold atezolizumab for up to 12 weeks after event onset. ^a • Refer patient to renal specialist. • Initiate treatment with corticosteroids equivalent to 1–2 mg/kg/day oral prednisone. • If event resolves to Grade 1 or better, resume atezolizumab. ^b • If event does not resolve to Grade 1 or better while withholding atezolizumab, permanently discontinue atezolizumab and contact Medical Monitor. ^c
Renal event, Grade 3 or 4	
 • Permanently discontinue atezolizumab and contact Medical Monitor. • Refer patient to renal specialist and consider renal biopsy. • Initiate treatment with corticosteroids equivalent to 1–2 mg/kg/day oral prednisone. • If event does not improve within 48 hours after initiating corticosteroids, consider adding an immunosuppressive agent. • If event resolves to Grade 1 or better, taper corticosteroids over ≥ 1 month.

^a Atezolizumab may be withheld for a longer period of time (i.e., > 12 weeks after event onset) to allow for corticosteroids (if initiated) to be reduced to the equivalent of ≤ 10 mg/day oral prednisone. The acceptable length of the extended period of time must be agreed upon by the investigator and the Medical Monitor.

^b If corticosteroids have been initiated, they must be tapered over ≥ 1 month to the equivalent of ≤ 10 mg/day oral prednisone before atezolizumab can be resumed.

^c Resumption of atezolizumab may be considered in patients who are deriving benefit and have fully recovered from the immune-mediated event. Patients can be re-challenged with atezolizumab only after approval has been documented by both the investigator (or an appropriate delegate) and the Medical Monitor.

Appendix 9

Risks Associated with Atezolizumab and Guidelines for Management of Adverse Events Associated with Atezolizumab (cont.)

IMMUNE-MEDIATED MYOSITIS

Immune-mediated myositis has been associated with the administration of atezolizumab. Myositis or inflammatory myopathies are a group of disorders sharing the common feature of inflammatory muscle injury; dermatomyositis and polymyositis are among the most common disorders. Initial diagnosis is based on clinical (muscle weakness, muscle pain, skin rash in dermatomyositis), biochemical (serum creatine kinase increase), and imaging (electromyography/MRI) features, and is confirmed with a muscle biopsy.

Patients with signs and symptoms of myositis, in the absence of an identified alternate etiology, should be treated according to the guidelines in [Table 13](#).

Table 13 Management Guidelines for Immune-Mediated Myositis

Event	Management
Immune-mediated myositis, Grade 1	
 • Continue atezolizumab. • Refer patient to rheumatologist or neurologist. • Initiate treatment as per institutional guidelines.
Immune-mediated myositis, Grade 2	
 • Withhold atezolizumab for up to 12 weeks after event onset^a and contact Medical Monitor. • Refer patient to rheumatologist or neurologist. • Initiate treatment as per institutional guidelines. • Consider treatment with corticosteroids equivalent to 1–2 mg/kg/day IV methylprednisolone and convert to 1–2 mg/kg/day oral prednisone or equivalent upon improvement. • If corticosteroids are initiated and event does not improve within 48 hours after initiating corticosteroids, consider adding an immunosuppressive agent. • If event resolves to Grade 1 or better, resume atezolizumab.^b • If event does not resolve to Grade 1 or better while withholding atezolizumab, permanently discontinue atezolizumab and contact Medical Monitor.^c

^a Atezolizumab may be withheld for a longer period of time (i.e., > 12 weeks after event onset) to allow for corticosteroids (if initiated) to be reduced to the equivalent of ≤ 10 mg/day oral prednisone. The acceptable length of the extended period of time must be agreed upon by the investigator and the Medical Monitor.

^b If corticosteroids have been initiated, they must be tapered over ≥ 1 month to the equivalent of ≤ 10 mg/day oral prednisone before atezolizumab can be resumed.

^c Resumption of atezolizumab may be considered in patients who are deriving benefit and have fully recovered from the immune-mediated event. Patients can be re-challenged with atezolizumab only after approval has been documented by both the investigator (or an appropriate delegate) and the Medical Monitor.

Appendix 9

Risks Associated with Atezolizumab and Guidelines for Management of Adverse Events Associated with Atezolizumab (cont.)

Table 13 Management Guidelines for Immune-Mediated Myositis (cont.)

Immune-mediated myositis, Grade 3	
 • Withhold atezolizumab for up to 12 weeks after event onset ^a and contact Medical Monitor. • Refer patient to rheumatologist or neurologist. • Initiate treatment as per institutional guidelines. • Respiratory support may be required in more severe cases. • Initiate treatment with corticosteroids equivalent to 1–2 mg/kg/day IV methylprednisolone, or higher-dose bolus if patient is severely compromised (e.g., cardiac or respiratory symptoms, dysphagia, or weakness that severely limits mobility); convert to 1–2 mg/kg/day oral prednisone or equivalent upon improvement. • If event does not improve within 48 hours after initiating corticosteroids, consider adding an immunosuppressive agent. • If event resolves to Grade 1 or better, resume atezolizumab. ^b • If event does not resolve to Grade 1 or better while withholding atezolizumab, permanently discontinue atezolizumab and contact Medical Monitor. ^c • For recurrent events, treat as a Grade 4 event.
Immune-mediated myositis, Grade 4	
 • Permanently discontinue atezolizumab and contact Medical Monitor. ^c • Refer patient to rheumatologist or neurologist. • Initiate treatment as per institutional guidelines. • Respiratory support may be required in more severe cases. • Initiate treatment with corticosteroids equivalent to 1–2 mg/kg/day IV methylprednisolone, or higher-dose bolus if patient is severely compromised (e.g., cardiac or respiratory symptoms, dysphagia, or weakness that severely limits mobility); convert to 1–2 mg/kg/day oral prednisone or equivalent upon improvement. • If event does not improve within 48 hours after initiating corticosteroids, consider adding an immunosuppressive agent. • If event resolves to Grade 1 or better, taper corticosteroids over ≥ 1 month.

^a Atezolizumab may be withheld for a longer period of time (i.e., > 12 weeks after event onset) to allow for corticosteroids (if initiated) to be reduced to the equivalent of ≤ 10 mg/day oral prednisone. The acceptable length of the extended period of time must be agreed upon by the investigator and the Medical Monitor.

^b If corticosteroids have been initiated, they must be tapered over ≥ 1 month to the equivalent of ≤ 10 mg/day oral prednisone before atezolizumab can be resumed.

^c Resumption of atezolizumab may be considered in patients who are deriving benefit and have fully recovered from the immune-mediated event. Patients can be re-challenged with atezolizumab only after approval has been documented by both the investigator (or an appropriate delegate) and the Medical Monitor.

Appendix 9

Risks Associated with Atezolizumab and Guidelines for Management of Adverse Events Associated with Atezolizumab (cont.)

HEMOPHAGOCYTIC LYMPHOHISTIOCYTOSIS AND MACROPHAGE ACTIVATION SYNDROME

Immune-mediated reactions may involve any organ system and may lead to hemophagocytic lymphohistiocytosis (HLH) and macrophage activation syndrome (MAS), which are considered to be potential risks for atezolizumab.

Patients with suspected HLH should be diagnosed according to published criteria by McClain and Eckstein (2014). A patient should be classified as having HLH if five of the following eight criteria are met:

- Fever $\geq 38.5^{\circ}\text{C}$
- Splenomegaly
- Peripheral blood cytopenia consisting of at least two of the following:
 - Hemoglobin < 90 g/L (9 g/dL) (< 100 g/L [10 g/dL] for infants < 4 weeks old)
 - Platelet count $< 100 \times 10^9/\text{L}$ (100,000/ μL)
 - ANC $< 1.0 \times 10^9/\text{L}$ (1000/ μL)
- Fasting triglycerides > 2.992 mmol/L (265 mg/dL) and/or fibrinogen < 1.5 g/L (150 mg/dL)
- Hemophagocytosis in bone marrow, spleen, lymph node, or liver
- Low or absent natural killer cell activity
- Ferritin > 500 mg/L (500 ng/mL)
- Soluble interleukin 2 (IL-2) receptor (soluble CD25) elevated ≥ 2 standard deviations above age-adjusted laboratory-specific norms

Patients with suspected MAS should be diagnosed according to published criteria for systemic juvenile idiopathic arthritis by Ravelli et al. (2016). A febrile patient should be classified as having MAS if the following criteria are met:

- Ferritin > 684 mg/L (684 ng/mL)
- At least two of the following:
 - Platelet count $\leq 181 \times 10^9/\text{L}$ (181,000/ μL)
 - AST ≥ 48 U/L
 - Triglycerides > 1.761 mmol/L (156 mg/dL)
 - Fibrinogen ≤ 3.6 g/L (360 mg/dL)

Patients with suspected HLH or MAS should be treated according to the guidelines in [Table 14](#).

Appendix 9

Risks Associated with Atezolizumab and Guidelines for Management of Adverse Events Associated with Atezolizumab (cont.)

Table 14 Management Guidelines for Suspected Hemophagocytic Lymphohistiocytosis or Macrophage Activation Syndrome

Event	Management
Suspected HLH or MAS	
 • Permanently discontinue atezolizumab and contact Medical Monitor. • Consider patient referral to hematologist. • Initiate supportive care, including intensive care monitoring if indicated per institutional guidelines. • Consider initiation of IV corticosteroids and/or an immunosuppressive agent. • If event does not improve within 48 hours after initiating corticosteroids, consider adding an immunosuppressive agent. • If event resolves to Grade 1 or better, taper corticosteroids over ≥ 1 month.

HLH = hemophagocytic lymphohistiocytosis; MAS = macrophage activation syndrome.

REFERENCES

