5.3.5.1 Diagnosis versus Signs and Symptoms

For adverse events, a diagnosis (if known) should be recorded on the Adverse Event eCRF rather than individual signs and symptoms (e.g., record only liver failure or hepatitis rather than jaundice, asterixis, and elevated transaminases). However, if a constellation of signs and/or symptoms cannot be medically characterized as a single diagnosis or syndrome at the time of reporting, each individual event should be recorded on the Adverse Event eCRF. If a diagnosis is subsequently established, all previously reported adverse events based on signs and symptoms should be nullified and replaced by one adverse event report based on the single diagnosis, with a starting date that corresponds to the starting date of the first symptom of the eventual diagnosis.

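### Both ferritin thresholds in Protocol Appendix 9 (HLH and MAS) are printed in two units that differ 1000-fold

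*Protocol*

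**What the plan says.** The HLH and MAS part of Protocol Appendix 9 gives two working definitions.

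- **HLH:** "A patient should be classified as having HLH if five of the following eight criteria are met". One of the eight is "Ferritin > 500 mg/L (500 ng/mL".
- **MAS:** "A febrile patient should be classified as having MAS if the following criteria are met". The first is "Ferritin > 684 mg/L (684 ng/mL", which is required. At least two of four further items (platelets, AST, triglycerides, fibrinogen) must also be met.

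Both lists are introduced as taken from published sources. For HLH, "Patients with suspected HLH should be diagnosed according to published criteria"; for MAS, "Patients with suspected MAS should be diagnosed according to published criteria for systemic juvenile idiopathic arthritis". Management is then tied to suspicion: "Patients with suspected HLH or MAS should be treated according to the guidelines in" Table 14, whose first step is permanent discontinuation of atezolizumab.

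Section 5.1.1 names HLH and MAS as potential risks of the drug and refers the reader to Appendix 9. The SAP contains no ferritin threshold.

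**The concern.** Elsewhere in these two lists the bracketed value is a conversion of the value before it. In the two ferritin lines the numeral stays the same while the unit changes from mg/L to ng/mL, which cannot be right because those units differ by a factor of 1000. The two printed thresholds in each line therefore define different sets of patients.

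The mg/L figure comes first. A site that applied it literally would require ferritin 1000 times higher than a site that applied the bracketed figure. The stake is the recorded diagnosis. Section 5.3.5.1 says "For adverse events, a diagnosis (if known) should be recorded on the Adverse Event eCRF rather than individual signs and symptoms", so a misapplied criterion could change the adverse event term, and Section 5.7 assesses the expectedness of serious events from there.

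**Working it through.** **Inputs.** All thresholds are from Protocol Appendix 9, HLH and MAS lists. Conversions: 1 mg/L = 10^6 ng per 1000 mL = 1000 ng/mL; 1 μg/L = 10^3 ng per 1000 mL = 1 ng/mL.

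**1. The ferritin pairs.**

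| List | First unit, converted | Printed in brackets | Ratio |
|---|---|---|---|
| HLH | 500 mg/L × 1000 = 500,000 ng/mL | 500 ng/mL | 1000 |
| MAS | 684 mg/L × 1000 = 684,000 ng/mL | 684 ng/mL | 1000 |

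Neither pair reproduces. With μg/L in place of mg/L, both do: 500 μg/L = 500 ng/mL and 684 μg/L = 684 ng/mL. Keeping mg/L and the bracketed values would need 0.5 and 0.684 mg/L.

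**2. The other nine pairs, as a control.**

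| Item | First unit | Bracket | Agrees |
|---|---|---|---|
| Hemoglobin (HLH) | 90 g/L | 9 g/dL | yes |
| Hemoglobin, infants (HLH) | 100 g/L | 10 g/dL | yes |
| Platelets (HLH) | 100 × 10^9/L | 100,000/μL | yes |
| ANC (HLH) | 1.0 × 10^9/L | 1000/μL | yes |
| Triglycerides (HLH) | 2.992 mmol/L | 265 mg/dL | yes |
| Fibrinogen (HLH) | 1.5 g/L | 150 mg/dL | yes |
| Platelets (MAS) | 181 × 10^9/L | 181,000/μL | yes |
| Triglycerides (MAS) | 1.761 mmol/L | 156 mg/dL | yes |
| Fibrinogen (MAS) | 3.6 g/L | 360 mg/dL | yes |

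Seven of these follow from metric prefixes alone. The triglyceride pairs need a molar factor that the documents do not give. Taking 88.57 mg/dL per mmol/L as an assumption, 2.992 × 88.57 = 265.0 and 1.761 × 88.57 = 156.0. Without any assumed factor, the two pairs imply nearly the same one: 265/2.992 = 88.57 and 156/1.761 = 88.59.

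Result: 9 of 11 pairs agree and 2 of 11 are off by exactly 1000.

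**3. Who would be classified differently.**

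*HLH (five of eight needed).* Take a patient with ferritin above 500 and up to 500,000 ng/mL who meets k of the other seven criteria. The ng/mL reading counts k + 1; the mg/L reading counts k.

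- k ≥ 5: HLH under both.
- k ≤ 3: at most 4 criteria, so HLH under neither.
- k = 4: 5 criteria against 4, so HLH under ng/mL only.

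*MAS (ferritin required).* Every febrile patient with at least two of the four other items and ferritin above 684 and up to 684,000 ng/mL has MAS under ng/mL and does not under mg/L.

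**The case against.** The arithmetic is not in dispute. The case against making anything of it has three parts.

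**It may be a text-reading fault.** Equal numerals either side of the bracket are what one misread character, μ to m, would produce. The surviving micro signs in the same lists are all in /μL, and those in Section 3.3.6 are in μg/mL; no intact μg/L is available for comparison. The supplied text has other one-letter oddities, such as ACCL for ACCI in SAP Section 4.3. This stands in part. A fault that hit both ferritin lines and spared every other micro sign in the two lists is unlikely, but only the source file can exclude it.

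**The correct unit cannot be proved from the documents.** This stands. The nine agreeing pairs show that each pair was meant to be equivalent, but not which ferritin unit is right. The cited criteria are not available here.

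**Nothing in the trial depends on it.** Most of this stands.

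- The ng/mL value is on the same line and the lead-ins cite published criteria.
- Table 14 acts on suspicion, so no treatment step changes.
- Ferritin is not among the laboratory tests in Section 4.5.6, and Section 5.2.3 does not name HLH or MAS as events of special interest.
- Section 5.3.5.1 falls back on signs and symptoms when no diagnosis is known, so the event would still be captured.
- Treatment lasts at most one year (Section 4.3.2.1), and the DFS analysis comes at least 12 months after the last enrollment (Section 6.1.2). Few if any patients should still be on drug after that analysis.

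These points limit the importance of the error. They do not make the printed lines consistent, and the lines are stated as classification rules for a named risk.

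**Conclusion.** The point holds as a low-severity correction. As printed, both ferritin thresholds contradict themselves 1000-fold, and neither document corrects them. Read in mg/L, the required MAS criterion would exclude essentially every patient it is meant to identify, and HLH would be missed in patients who meet exactly four of the other seven criteria. No treatment step, endpoint, alpha level, sample size or SAP analysis is affected.

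The inconsistency itself rests on unit conversion alone. Two further judgments carry some doubt, so overall confidence is medium: that the fault lies in the protocol and not in the text extraction, and that ng/mL (equivalently μg/L) is the intended unit. How often a site would use the mg/L figure cannot be estimated from the documents.

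**What to change.** First check the two lines in the protocol source file and against the two cited sets of criteria. If they confirm the ng/mL values, replace mg/L with μg/L in both ferritin lines of Appendix 9, so that they read 500 μg/L (500 ng/mL) and 684 μg/L (684 ng/mL). The cost is two unit corrections, which can go into the next amendment. Design, data collection and analysis are unchanged.
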